## **2.2 Hypothesis and Specific Aims:**

We hypothesize that there are differences in patient-centered clinical outcomes and Patient Reported Outcomes (PROs) between women who choose GCC versus AS, and that these differences can be compared using advanced analytic methods to allow for the expected treatment selection biases between groups.

The specific aims of this study are the following:

**Aim 1. Compare patient-reported outcomes (PROs) between patients diagnosed with ductal carcinoma in situ (DCIS) who received GCC to patients diagnosed with DCIS who underwent AS as well as those diagnosed with atypical ductal hyperplasia (ADH), and lobular carcinoma in situ LCIS/atypical lobular hyperplasia (ALH) (as proxies for DCIS active surveillance (AS) group) in a cross-sectional patient cohort at 6 selected study sites.**

PROs will be collected from surveys administered to patients diagnosed for either DCIS, ADH, LCIS, or ALH between January 1, 2012 and June 30, 2017 at each of six study sites: Duke University Medical Center (DUMC), Dana-Farber Cancer Institute (DFCI), MD Anderson Cancer Center (MDACC), Massachusetts General Hospital (MGH), Newton Wellesley Hospital (NWH), and Dana-Farber/Brigham and Women's Cancer Center (DF/BWCC) in clinical affiliation with South Shore Hospital (DFCI @ SSH). We are planning for survey data collection to begin in September 2017, but will officially commence upon IRB approval at each recruiting site. MDACC received their site's IRB approval on December 6, 2017 and has now been added to the DFCI IRB as a site. MDACC will now complete applicable study procedures as outlined in this protocol. DUMC received their site's IRB approval on February 27, 2018 and has now been added to the DFCI IRB as a site. Duke will now complete study procedures as outlined in this protocol. MGH has been added to the DFCI IRB as a site. MGH will now complete study procedures as outlined in this protocol. DFCI @ SSH has been added to the DFCI IRB as a site. DFCI @ SSH will now complete study procedures as outlined in this protocol. The DFCI study team will complete all patient recruitment steps for DFCI @ SSH. NWH has been added to the DFCI IRB as a site. NWH will now complete study procedures as outlined in this protocol.

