### **3.0 RESEARCH SUBJECT SELECTION:**

This study will be conducted at 6 NCI Comprehensive Cancer Center sites (DUMC, DFCI, MDACC, MGH, NWH, and DFCI @ SSH). Additional study sites may be considered to enhance accrual.

The GCC group will be those patients diagnosed with DCIS and treated according to one of the standard treatment options for DCIS (Table 1). Importantly, since only 2-3% of all women diagnosed with DCIS are offered and/or undergo active surveillance, there are insufficient numbers of women with DCIS solely electing AS to compare with women treated according to GCC, even across 3 large volume cancer centers. Therefore, we decided to add to our DCIS AS group, those patients who have a similarly high breast cancer risk based on a diagnosis of ADH, ALH, or LCIS for whom the routine recommendation is active surveillance. The ADH/ALH/LCIS group will thus serve as an additional proxy for the DCIS active surveillance group, since these risk lesions are managed with a follow up and surveillance approach as could be applied if AS were to be used for low risk DCIS. This design will allow the most relevant comparison of PROs between GCC and AS strategies for conditions associated with increased breast cancer risk.

English and Spanish speaking patients diagnosed for either: DCIS, ADH, ALH and/or LCIS between 2012 and 2016 will be included. Each site has a large patient volume of DCIS cases treated and specific expertise in studying a DCIS patient population. Moreover, the sites have unique and complementary patient populations, with a large African American population treated at DUMC (26.7% of all patients with DCIS treated 2011-2013) and a sizable Hispanic population treated at MDACC (12.8% of all patients with DCIS treated 2011-2013).

***Eligibility Criteria.*** Patients treated at DUMC, DFCI, MDACC, MGH, NWH, or DFCI @ SSH with a diagnosis of DCIS, LCIS, ADH, or ALH who are also:

- Age 18 or more at index diagnosis
- Diagnosed with DCIS, LCIS, ADH, or ALH (the most recent, highest risk lesion is the “index lesion”) between January 1, 2012 and June 30, 2017
- Able to read either English or Spanish and able to provide written (via paper), verbal consent or on-line informed consent
- Treated and followed at one of the study sites (including affiliated network sites) and for whom treatment and surveillance data are available, for at least 1 year of follow up after date of diagnosis

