#### **4.0 RESEARCH SUBJECT ENTRY**

All activities will be conducted through the 6 study recruitment sites, who will handle all eligibility for their own site's patients. The DFCI main study site will screen and recruit for its own patients as well as for DFCI @ SSH patients. Patients will be recruited individually to the trial. All women with DCIS, LCIS, ADH or ALH newly diagnosed between January 1, 2012 and June 30, 2017 and treated at one of the 6 designated study sites will be identified systematically at each study site using cancer registry and clinic, radiology, and pathology record review. We will collect consecutive cases in a retrograde fashion starting from June 30, 2017 to January 1, 2012 until we have collected 900 DCIS cases and 300 LCIS, ADH, or ALH cases.

In order to assess eligibility and initiate entry into the study chart review necessary for Aim 1 of the study, we will request approval of a waiver of informed consent and a waiver of HIPPA. Once approved, a research coordinator at each site will review clinic, radiology, pathology, and tumor registry lists to screen for potential candidates, and identify potentially eligible patients. We will extract the following from the medical record for potential participants:

- Name
- Contact information (i.e. mail address, phone number and/or email address)
- Age
- Race/Ethnicity
- Date and type of last biopsy
- Date and type of last surgery
- How lesion identified and relevant mammography
- Pathologic features of the disease on core biopsy (if DCIS: grade, necrosis, ER, PR/HER2 if done, size, microinvasion)
- Type of subsequent evaluation of lesion (excision, surgery etc.) and any subsequent breast pathology or procedure
- Any adjuvant treatment
- Date and vital status at last follow-up; we will plan to complement this with a National Death Index (NDI)/Institutional database look to make sure potential participants are available before contacting them.

Sites responsible for screening patients and their affiliates will use the eligibility information above for their patients to determine eligibility. We will also use these data to describe the patient population and the disease characteristics of these non-invasive breast lesions at diagnosis.

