### **5.2 Selection of Instruments**

***Rationale for participant selection and survey methodology.*** Although we recognize that issues of decision-making and treatment selection are more salient closer to the date of diagnosis when these decisions take place, the short timeframe of the project period limits the number of cases that could be identified and surveyed within the timeframe of the study. Therefore, we are reviewing contemporary cases diagnosed from 2012 to 2016 for eligibility. The advantage of this design is that it allows us to assess QOL after diagnosis and treatment in a large group of patients, and provides a more cost-effective approach compared to rapid case ascertainment. Moreover, this design will allow collection of our primary endpoint of persistent, rather than postoperative, pain among the participants, as well as several secondary endpoints, including health-related and psychosocial QOL, anxiety, depression, and intolerance of uncertainty among patients at a range of time in follow-up.

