### **6.2 Sample size and statistical power**

Importantly, published data indicate that patients undergoing lumpectomy with radiation report comparable levels of pain and sensory disturbances as those undergoing mastectomy. Thus, these treatment groups will be grouped together in the initial analysis, then a stratified analysis will be performed. Preliminary data among 582 women undergoing either lumpectomy or mastectomy indicate that the mean persistent pain intensity after breast surgery is 2.61 (DS 4.24). Given a sample size of 900 patients in the GCC group and 300 in the AS group, we will be able to detect with 90% power at a level of 0.05 (2-sided) a difference in pain intensity score of 2 (from 2.61 to 0.61), which has been deemed to be a clinically meaningful difference.

Based upon the number of unique cases diagnosed with DCIS at each site between 2010 and 2013, we estimate that at all 6 study sites combined, approximately 1500 women will have been diagnosed with DCIS between January 1, 2012 and June 30, 2017 and will be eligible to participate. Our response rate in prior survey studies has been approximately 60% using the approach we will adapt to the current study; thus, we anticipate that about 900 women with DCIS will be accrued and will complete the survey across all study sites. These patients will be matched 3:1 to participants diagnosed with ADH or LCIS/ALH undergoing active surveillance. DCIS participants will be matched 3:1 to ADH/LCIS/ALH participants, based on matching criteria of age within 5 years, year of diagnosis, and study site. Additional matching criteria such as race, income, highest education level attained, and family history of breast cancer will be considered based upon stakeholder input during the protocol preparation process.

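### The primary pain endpoint is named in three ways, and if persistent pain is meant, no rule on time since last breast surgery secures it

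*Protocol*

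**What the plan says.** Three sections describe the primary pain outcome differently. Section 1.1 refers to chronic pain severity. Section 2.2, under Aim 1, calls the outcome postoperative pain. Section 5.2 justifies the design because it captures "our primary endpoint of persistent, rather than postoperative, pain among the participants". Section 6.2, repeated in the SAP, builds its power statement on a "mean persistent pain intensity after breast surgery is 2.61 (DS 4.24"), so it too assumes persistent pain.

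The instrument paragraph of Section 5.2 defines the measure as worst pain severity plus the Pain Burden Index. It gives no minimum duration of pain and no minimum time since an operation. Section 5.1 describes a single cross-sectional survey.

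On timing, the eligibility list in Section 3.0 requires that a woman be one "for whom treatment and surveillance data are available, for at least 1 year of follow up after date of diagnosis". Section 4.0 has each site extract "Date and type of last surgery" from the record. That item does not reappear in the exclusions, in the matching factors of Section 6.2 (age, diagnosis year, site), or among the treatment and comorbidity factors that Section 6.3 names for confounding control.

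**The concern.** A one-time survey cannot show persistence by repeated measurement. It can do so only through the wording of the question or through a rule on elapsed time since surgery. The elapsed-time rule in the plan is tied to the wrong event: a woman can be years past diagnosis and weeks past a breast operation.

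The documents make later operations plausible. The GCC options include mastectomy, Section 1.2 notes growing use of bilateral mastectomy, and the appendix list includes a BREAST-Q form for mastectomy with reconstruction. Metachronous disease is eligible, and the chart form records subsequent breast procedures. Staged reconstruction, revision and contralateral surgery are the obvious routes.

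At stake is what the result may be called. If recovery from recent surgery is mixed in, the GCC mean, and probably the GCC-AS difference, cannot be read as persistent pain, which is the harm that Section 5.2 says the design captures.

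**Working it through.** **1. The plan's own power figure.** Inputs from Section 6.2: 900 GCC, 300 AS, SD 4.24, difference 2 points, two-sided 0.05.

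- SE = 4.24 × √(1/300 + 1/900) = 0.283.
- Power = Φ(2/0.283 − 1.96) = Φ(5.12), above 99.99%. The stated 90% does not reproduce. The discrepancy is conservative and a separate matter.
- Difference detectable at 90% power = (1.960 + 1.282) × 0.283 = 0.92 points. Differences well below 2 points can therefore reach significance, so a bias of a few tenths of a point is not irrelevant.

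**2. What the 1-year clock guarantees.** An operation done m months after diagnosis is at least 12 − m months old at the survey. It is under 6 months old at the 1-year mark only if m exceeds 6, and under 3 months old only if m exceeds 9. Most index operations should therefore be well in the past. The exposure comes mainly from later procedures, for which the clock guarantees nothing.

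**3. Size of the bias.** Bias = (share of GCC recently operated on − share of AS recently operated on) × excess pain score. The documents give none of these three inputs. Assumed ranges: GCC share 2–20%, AS share zero or half the GCC share, excess 1–3 points. The last column is the two-sided rejection rate when the true difference is zero.

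| GCC share | AS share | Excess | Bias (points) | Bias / SE | False-positive rate |
|---|---|---|---|---|---|
| 2% | 1% | 1 | 0.01 | 0.04 | 5.0% |
| 5% | 0% | 2 | 0.10 | 0.35 | 6.4% |
| 10% | 5% | 2 | 0.10 | 0.35 | 6.4% |
| 10% | 0% | 2 | 0.20 | 0.71 | 10.9% |
| 20% | 10% | 2 | 0.20 | 0.71 | 10.9% |
| 20% | 0% | 3 | 0.60 | 2.12 | 56.5% |

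For the 10% / 0% / 2-point row: 0.10 × 2 = 0.20; 0.20/0.283 = 0.71; 1 − Φ(1.96 − 0.71) + Φ(−1.96 − 0.71) = 0.109. With equal shares and equal excess in the two groups, the net bias is zero.

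**4. Precision of a restricted analysis.** Assume that 5–30% of GCC women are left out and all 300 AS women stay.

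- 855 GCC remain: SE = 4.24 × √(1/300 + 1/855); detectable difference 0.92.
- 630 GCC remain: SE = 4.24 × √(1/300 + 1/630) = 0.297; detectable difference 0.96.
- If AS also lost half that share (15%, leaving 255): SE = 4.24 × √(1/255 + 1/630) = 0.315; detectable difference 3.242 × 0.315 = 1.02.

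All of these lie far below 2 points.

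**The case against.** The strongest reply is that contamination is possible but not shown. The index operation will usually be many months old. Recurrent or progressive DCIS is excluded, and the index lesion is the most recent highest-risk one, so some routes to later surgery are closed or restart the clock. The survey itself is not in the available text and may ask about onset or timing. All of this stands, and it is why the size is given only as an assumed range. Even so, no analysis step uses timing information from either the survey or the chart.

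A second reply concerns the remedy. Later reconstruction or revision follows from choosing GCC, so removing those women conditions on a post-treatment event and could understate harm. This also stands. It argues against replacing the all-women analysis with a restricted one, but not against reporting both.

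Two stronger readings are tempting but unsupported:

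- A reader might infer that the error can only run against GCC. The chart form records excision and surgery for every lesion type, and metachronous disease is eligible in both groups. Only the difference between groups produces bias.
- A reader might infer from the sampling order ("We will collect consecutive cases in a retrograde fashion starting from June 30, 2017 to January 1, 2012") and the planned start ("We are planning for survey data collection to begin in September 2017") that women fresh from primary treatment enter the endpoint. Women short of 1 year of follow-up are ineligible under Section 3.0. The latest diagnoses reach 1 year on June 30, 2018, within a recruitment phase expected to end in 2019, and sites start only after their own IRB approval. The order is an operational mismatch and no evidence of bias.

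**Conclusion.** The point holds in a limited form. The three descriptions of the endpoint contradict one another and must be reconciled. If persistent pain is intended, as Section 5.2 and the power assumption imply, the design does not secure it: eligibility is timed from diagnosis, and the collected surgery date is unused.

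The probable direction is an inflated GCC-AS difference, because later breast surgery is likely to be more common in GCC. That direction is a judgement, since the documents give no rates. Across the assumed inputs the spurious difference runs from 0.01 to 0.60 points. The middle case of 0.20 points is one tenth of the 2-point target, so this alone would not create a clinically meaningful difference. It could affect the significance of a smaller one, and it decides whether the result may be labelled persistent pain.

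**What to change.** 1. Reconcile Sections 1.1, 2.2 and 5.2 on one name and definition for the primary pain endpoint.
2. If it is persistent pain, state what makes it so: a minimum interval since the last breast or axillary surgery, chosen by the sponsor.
3. Derive time since last surgery at the survey date from the chart, updated while records are still being accessed. The screening date alone can be stale: the contact schedule in Section 4.0 allows 2 weeks for the physician, 8 for the invitation and 6 for survey reminders, or 16 weeks in all.
4. In SAP Section 6.3, prespecify the pain comparison among women beyond the interval, by the same rule in both groups, alongside the all-women comparison. Write down beforehand what counts as agreement, and describe the result as persistent pain only if the two agree.
5. As housekeeping, align the start of the retrograde list in Section 4.0 with the 1-year rule.

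The cost is one derived variable, a chart update, and fewer women in the restricted analysis. Leaving out 5–30% of GCC moves the difference detectable at 90% power from 0.92 to at most 0.96 points, or to about 1.02 if AS also loses 15%. Operations done at other hospitals may be missing from the chart, which should be reported as a limitation. No new survey item is needed.

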#### ***Exclusion criteria***

- Ever had a diagnosis of invasive or microinvasive breast cancer
- DCIS prior to index lesion or history of progressive/recurrent DCIS after treatment
- Other cancers (excluding non-melanoma skin cancer) diagnosed within 5 years prior to index

lesion, including concurrent invasive cancer diagnosis and up to the present time of participant's approach to invitation into the study

- Patients identified by treating physician as being unsuitable for contact

#### **4.0 RESEARCH SUBJECT ENTRY**

All activities will be conducted through the 6 study recruitment sites, who will handle all eligibility for their own site's patients. The DFCI main study site will screen and recruit for its own patients as well as for DFCI @ SSH patients. Patients will be recruited individually to the trial. All women with DCIS, LCIS, ADH or ALH newly diagnosed between January 1, 2012 and June 30, 2017 and treated at one of the 6 designated study sites will be identified systematically at each study site using cancer registry and clinic, radiology, and pathology record review. We will collect consecutive cases in a retrograde fashion starting from June 30, 2017 to January 1, 2012 until we have collected 900 DCIS cases and 300 LCIS, ADH, or ALH cases.

In order to assess eligibility and initiate entry into the study chart review necessary for Aim 1 of the study, we will request approval of a waiver of informed consent and a waiver of HIPPA. Once approved, a research coordinator at each site will review clinic, radiology, pathology, and tumor registry lists to screen for potential candidates, and identify potentially eligible patients. We will extract the following from the medical record for potential participants:

- Name
- Contact information (i.e. mail address, phone number and/or email address)
- Age
- Race/Ethnicity
- Date and type of last biopsy
- Date and type of last surgery
- How lesion identified and relevant mammography
- Pathologic features of the disease on core biopsy (if DCIS: grade, necrosis, ER, PR/HER2 if done, size, microinvasion)
- Type of subsequent evaluation of lesion (excision, surgery etc.) and any subsequent breast pathology or procedure
- Any adjuvant treatment
- Date and vital status at last follow-up; we will plan to complement this with a National Death Index (NDI)/Institutional database look to make sure potential participants are available before contacting them.

Sites responsible for screening patients and their affiliates will use the eligibility information above for their patients to determine eligibility. We will also use these data to describe the patient population and the disease characteristics of these non-invasive breast lesions at diagnosis.

For each eligible case determined through this rigorous review, the institutional attending physician will be notified by email about the study and the plans to invite the patient to participate in the survey study. Staff at each study site or the lead site for affiliates will contact the treating physician to ask them to indicate if they have any concerns about contacting this patient for the study. If the local treating physician does not indicate any potential problems with the selected patient's participation within 2 weeks, then the study coordinator at each site will verify the mailing address for each eligible patient.

Each site will send their own potential patients the study invitation letter (Appendix A) which will include information about the study, provide study contact information, and ask patients to respond, and if interested in participating in the study, write their email address, or alternative form of contact. Because people are busy and may respond to different forms of communication (i.e. calls, notes, letters, etc.), the local study team will follow up with 3 additional contacts over an 8-week time period (2 weeks (recontact), 4 weeks (call/resend) and 8 weeks (call/resend) to allow for sufficient time to respond. The DFIC study team will pilot two patient outreach materials from Patient Advocates—two brief notes—added to the invitation letter and survey to one hundred patients to test improved response and participation outcome. One or both of these outreach material, if proven effective, may be continued past the pilot one hundred patients. At the end of the recruitment period when no further new surveys are to be initiated, the DFCI study team will inform by mail, email, or phone any new patient who indicates interest to complete a survey that the study is closed and no new surveys will be initiated.

The DFCI study team has found this to be acceptable and desired in past survey research they have conducted. As noted above, initial contact will be made by each recruiting site for their own patients (e.g. MDA study team will contact MDA patients, Duke study team will contact Duke patients and DFCI study team will contact DFCI patients). Collaborating institutions may use waivers of consent and authorization to access patient study records to determine eligibility, collect data from the medical charts and to initiate patient contact for the prospective survey. The names and contact information of all women who agree to participate for the prospective component of this study (the survey) will be sent from the local team (MDACC, Duke, MGH, NWH, or DFCI @ SSH) to the DFCI study team. The DFCI study team will conduct all consenting and survey initiation/follow up, as described in section 5.5.1.

The DFCI study coordinator then will initiate the survey (Appendix B) online, paper or over the phone as requested by the participant. The majority of the surveys will be conducted in English, although a Spanish language paper version of Survey B.1 and B.2 will be available. There will be 3 potential recontact timepoints by the DFCI study staff to participants who do not complete the survey: 2 weeks (recontact), 4 weeks (call/resend) and 6 weeks (call/resend) from the initial mailing.

There are 3 modes in which an English-speaking patient can elect to complete the prospective survey: online, paper or phone. A Spanish speaking patient will have the paper survey available to select. Depending on the way the survey is completed, consent will be obtained accordingly. Please see section 5.5.1 for additional details.

Each site or the lead for an affiliate will track their own patients for eligibility and desire to participate (Appendix A). Sites will then pass contact information and approved CRF information for respondents who affirm interest on Appendix A to DFCI study staff. DFCI study staff then will follow up with patients for consenting and survey participation. See 5.5 Description of the study process for additional survey completion detail.

DFCI study staff will register all consenting participants (DF/HCC and non-DF/HCC) in the Clinical Trials Management System (CTMS) OnCore as required by DF/HCC SOP REGIST-101, but registration will occur once a consent has been obtained (paper consent, online elements of consent, verbal consent depending on modality of participant completion) and once the survey has been completed.

DFCI study staff will complete an eligibility checklist according to DF/HCC SOP REGIST-104, for all women who initiate a survey (any modality). If a participant completes a survey via RedCap, study staff will print out the page showing she checked the box saying she agrees to the elements of consent as the documentation of her consent. For participants who complete by paper, DFCI study staff will have participants sign an informed consent document. DFCI study staff will keep documentation of verbal consent for those giving consent over the telephone. DFCI study staff will collect and store participant consent forms and eligibility checklists. The Coordinating Center will provide a study number for all enrolled participants.

